## Appendix 7 Summary of Treatment and Food Restrictions

[figure not shown]
Treatment	During Treatment	Reason
Immunosuppressants other than those allowed by protocol	Prohibited	Interferes with study efficacy endpoints
Aminoglycosides Amphotericin B Melphalan Ketoconazole Rifampin	Prohibited	May potentiate toxicity
NSAIDs chronic dosing (>7 consecutive days)	Prohibited	May potentiate nephrotoxicity
P-gp substrates	To be monitored	Drug-drug interaction
P-gp inhibitors	To be discussed with Medical Monitor	Drug-drug interaction
Androgenic steroids Cimetidine Fluconazole, itraconazole Macrolide antibiotics (azithromycin, clarithromycin, erythromycin) Metoclopramide Barbiturates and derivatives Carbamazepine Octreotide acetate Phenytoin Sulfadimidine (intravenous) Theophylline	To be discussed with Medical Monitor	Drugs interfering with Orelvo metabolism
ACE inhibitors and ARBs	Change or commencement prohibited	Interfere with primary endpoint assessment
Foods Grapefruit and grapefruit juice	Prohibited	May affect the metabolism of Orelvo

[figure not shown]
Abbreviations: ACE = Angiotensin converting enzyme; ARB = Angiotensin receptor blocker; NSAID = Non-steroidal anti-inflammatory drug; Pgp- = P-glycoprotein.

Appendix 9 [REDACTED]

[REDACTED]

[REDACTED]

[REDACTED]

[REDACTED]

[REDACTED]

[REDACTED]

[REDACTED]

[REDACTED]

- [REDACTED]
- [REDACTED]
- [REDACTED]
- [REDACTED]
- [REDACTED]

[REDACTED]

[REDACTED]

[REDACTED]

[REDACTED]

[REDACTED]

[REDACTED]

[REDACTED]

[REDACTED]

[REDACTED]

10 REFERENCES37

QMD Ref: [REDACTED]	Effective: 12Aug2019	Governing QMD: [REDACTED]
Confidentiality Statement		
This document is the property of [REDACTED] and may not be duplicated, copied, altered or removed from company without prior approval from [REDACTED] or in compliance with [REDACTED].		

REF: [REDACTED]

		Controlled Quality Management Document	
		Sponsor:	Aurinia Pharmaceuticals
		Protocol Number:	AUR-VCS-2016-02
STATISTICAL ANALYSIS PLAN. PHASE 2-3-4			

LIST OF ABBREVIATIONS

AE	Adverse event
Anti-dsDNA	Anti-double-stranded deoxyribonucleic acid
AR	Auto Regressive
ATC	Anatomical Therapeutic Chemical Classification System
AURORA 1	Aurinia Orelvo Renal Assessments 1: Aurinia Renal Response in Active Lupus with Orelvo (voclosporin)
AURORA 2	Aurinia Orelvo Renal Assessments 2: Aurinia Renal Response in Lupus with Orelvo (voclosporin)
Aurinia	Aurinia Pharmaceuticals Inc.
BID	Twice daily
C3 / C4	Complement 3 / complement 4
CEC	Clinical Endpoints Committee
CI	Confidence interval
CTCAE	Common Terminology Criteria for Adverse Events
EAIR	Exposure-adjusted incidence rates
EDC	Electronic data capture
ECG	Electrocardiogram
eCRF	Electronic case report form
eGFR	Estimated glomerular filtration rate
FAS	Full analysis set
FMV	First morning void
HRQoL	Health-related quality of life
ITT	Intent-to-treat
IV	Intravenous
LN	Lupus nephritis
LS	Least Squares
MMF	Mycophenolate mofetil
MMRM	Mixed Effect Model Repeated Measures
OR	Odds ratio
Orelvo	Voclosporin (for Phase 3 lupus nephritis indication)
PK	Pharmacokinetic
QTc	Corrected QT interval
QTcF	QT interval duration corrected for heart rate using method of Fridericia
SAE	Serious adverse event
SAP	Statistical analysis plan
SELENA	Safety of Estrogens in Lupus Erythematosus National Assessment

QMD Ref: [REDACTED]	Effective: 12Aug2019	Governing QMD: [REDACTED]
Confidentiality Statement		
This document is the property of [REDACTED] and may not be duplicated, copied, altered or removed from company without prior approval from [REDACTED] or in compliance with [REDACTED].		

REF: [REDACTED]

		Controlled Quality Management Document	
		Sponsor:	Aurinia Pharmaceuticals
		Protocol Number:	AUR-VCS-2016-02
STATISTICAL ANALYSIS PLAN. PHASE 2-3-4			

SLE	Systemic lupus erythematosus
SLEDAI	Systemic Lupus Erythematosus Disease Activity Index
TEAE	Treatment-emergent adverse event
UPCR	Urine protein creatinine ratio

QMD Ref: [REDACTED]	Effective: 12Aug2019	Governing QMD: [REDACTED]
Confidentiality Statement		

1 INTRODUCTION

This document details the planned statistical analyses for the Aurinia Pharmaceuticals Inc. AUR-VCS-2016-02 (AURORA 2) study titled “A Randomized, Controlled, Double-blind Continuation Study Comparing the Long term Safety and Efficacy of Orelvo (voclosporin) (23.7 mg Twice Daily) with Placebo in Subjects with Lupus Nephritis”.

The proposed analyses are based on the contents of the final version of the protocol (Amendment 2, dated 21-DEC-2018).

Subjects who have completed 52 weeks of treatment with study drug in the AURORA 1 study will continue to receive the same treatment as assigned by randomization in the AURORA 1 study (either voclosporin or matching placebo) for up to an additional 24 months in AURORA 2.

After 12 months treatment in the AURORA 2 study (i.e., after 24 months treatment in total), subjects taking the 23.7 mg (3 capsules) twice daily (BID) dose will be permitted to reduce the dose of voclosporin to 15.8 mg (2 capsules) BID if considered appropriate by the Investigator and after consultation with the Medical Monitor.

Where a dose reduction is considered, the following guidance should be considered:

AURORA 2: Week 52 Dose	AURORA 2: Reduced Dose
23.7 mg BID and urine protein creatinine ratio (UPCR) \geq 1.5 mg/mg	No reduction
23.7 mg BID and UPCR <1.5 mg/mg	15.8 mg BID
<23.7 mg BID	No reduction

2 STUDY OBJECTIVES

2.1 Primary Objective

To assess the long-term safety and tolerability of voclosporin compared with placebo for up to an additional 24 months following completion of treatment in the AURORA 1 study in subjects with Lupus Nephritis (LN).

QMD Ref: [REDACTED]	Effective: 12Aug2019	Governing QMD: [REDACTED]
Confidentiality Statement		
This document is the property of [REDACTED] and may not be duplicated, copied, altered or removed from company without prior approval from [REDACTED] or in compliance with [REDACTED].		

REF: [REDACTED]

		Controlled Quality Management Document	
		Sponsor:	Aurinia Pharmaceuticals
		Protocol Number:	AUR-VCS-2016-02
STATISTICAL ANALYSIS PLAN. PHASE 2-3-4			

2.2 Secondary Objective

To assess the long-term efficacy of voclosporin compared with placebo for up to an additional 24 months following completion of treatment in the AURORA 1 study in subjects with LN.

3 ENDPOINTS

All estimands are assessed in all subjects who continued into the continuation study. Additional analyses will be performed to compare subjects who did not participate in AURORA 2 with those who participated.

3.1 Primary Endpoint

Adverse event (AE) profile and routine biochemical and hematological assessments. Estimand for AEs is the proportion of subjects reporting AEs in the Safety Population when comparing voclosporin and placebo at each visit. Estimands for biochemical and hematological assessments are the mean absolute values and mean changes from AURORA 1 baseline in the Safety Population when comparing voclosporin and placebo at each visit.

3.2 Secondary Endpoints

3.2.1 Key Secondary Endpoints

- Renal response at Months 12, 18, 24, 30 and 36. Estimand is the proportion of subjects showing renal response (programmed response) in the Intention-To-Treat (ITT) Population when comparing voclosporin and placebo at each visit. Renal response is defined as:
 - UPCR of ≤ 0.5 mg/mg
 - Estimated glomerular filtration rate (eGFR) ≥ 60 mL/min/1.73 m² or eGFR < 60 mL/min/1.73 m² with no confirmed decrease $> 20\%$ or eGFR < 60 mL/min/1.73 m² with confirmed decrease $> 20\%$ but with no disease-related or treatment-related eGFR associated AE present at time of assessment
 - Received no rescue medication for LN
 - Did not receive more than 10 mg prednisone for ≥ 3 consecutive days or for ≥ 7 days in total during the 8 weeks prior to the renal response assessment.
 - Subjects who withdraw from the study prior to the response assessment will be defined as non-responders.

QMD Ref: [REDACTED]	Effective: 12Aug2019	Governing QMD: [REDACTED]
Confidentiality Statement		
This document is the property of [REDACTED] and may not be duplicated, copied, altered or removed from company without prior approval from [REDACTED] or in compliance with [REDACTED].		
REF: [REDACTED]		Page 9 of 37

		Controlled Quality Management Document	
		Sponsor:	Aurinia Pharmaceuticals
		Protocol Number:	AUR-VCS-2016-02
STATISTICAL ANALYSIS PLAN. PHASE 2-3-4			

- Partial renal response at Months 12, 18, 24, 30 and 36 defined as a 50% reduction from baseline in UPCR. Estimand is the proportion of subjects showing partial renal response (programmed response) in the ITT Population when comparing voclosporin and placebo at each visit.
- Renal flare as adjudicated by the Clinical Endpoints Committee (CEC). Estimand is the proportion of subjects showing renal flare (CEC adjudicated response) in the ITT Population when comparing voclosporin and placebo at each visit.
- Extra-renal flare as adjudicated by the CEC. Estimand is the proportion of subjects showing extra-renal flare (CEC adjudicated response) in the ITT Population when comparing voclosporin and placebo at each visit.
- Safety of Estrogens in Lupus Erythematosus National Assessment- Systemic Lupus Erythematosus Disease Activity Index (SELENA-SLEDAI) scores by visit. Estimand is the mean change from AURORA 1 baseline in Total SELENA-SLEDAI score in the ITT Population when comparing voclosporin and placebo at each visit.
- Change in UPCR, eGFR, urine protein, and serum creatinine from AURORA 1 baseline by visit. Estimand is the mean change from AURORA 1 baseline in the ITT Population when comparing voclosporin and placebo at each visit.

3.2.2 Other Secondary Endpoints

- Change in immunology parameters complement 3 (C3), complement 4 (C4), and anti-double-stranded deoxyribonucleic acid (anti-dsDNA) from AURORA 1 baseline by visit. Estimand is the mean change from AURORA 1 baseline in the ITT Population when comparing voclosporin and placebo at each visit. It is assessed in all subjects who continued into the continuation study.
- Change in health-related quality of life (HRQoL) (SF-36) from AURORA 1 baseline by visit. Estimand is the mean change from AURORA 1 baseline in the ITT Population when comparing voclosporin and placebo at each visit. It is assessed in all subjects who continued into the continuation study.
- Healthcare Resource Utilization (HRU). Estimand is the proportion of subjects reporting healthcare resource utilization in the ITT Population when comparing voclosporin and placebo at each visit. It is assessed in all subjects who continued into the continuation study.

QMD Ref: [REDACTED]	Effective: 12Aug2019	Governing QMD: [REDACTED]
Confidentiality Statement		
This document is the property of [REDACTED] and may not be duplicated, copied, altered or removed from company without prior approval from [REDACTED] or in compliance with [REDACTED].		

REF: [REDACTED]

		Controlled Quality Management Document	
		Sponsor:	Aurinia Pharmaceuticals
		Protocol Number:	AUR-VCS-2016-02
STATISTICAL ANALYSIS PLAN. PHASE 2-3-4			

4 SAMPLE SIZE

Eligible subjects will enter this study from the AURORA 1 study in order to provide the opportunity of an additional 24 months of treatment (total of 36 months of treatment); no sample size calculation is required.

5 RANDOMIZATION

Subjects continue on the same treatment which they received in AURORA 1.

6 PLANNED ANALYSES

No statistical analysis plan (SAP) prepared in advance of the data can be absolutely definitive and the final Clinical Study Report (CSR) may contain additional tables or statistical tests if warranted by the data obtained. The justification for any such additional analyses will be fully documented in the final CSR.

6.1 Analysis Populations

6.1.1 Intent-to-Treat Population

The ITT population will be based on ITT principles and will consist of all subjects who are consented to treatment in AURORA 2 (n=216). This group will be analyzed based on the treatment to which the subject was randomized in the AURORA 1 study.

6.1.2 Safety Population

The safety population will consist of all subjects who receive at least 1 dose of study drug in the AURORA 2 study (n=216). The subjects in this group will be analyzed based on the treatment they received. Subjects who receive voclosporin treatment for more than 14 days will be assigned to the voclosporin arm irrespective of the arm they were randomized to.

Additional safety populations will be defined as follows:

- AURORA 1 safety population (all subjects who were treated in core study, n=356) and
- subjects who did not participate in AURORA 2 (n=140).

6.2 Derived Data

This section describes the derivations required for statistical analysis. Unless otherwise stated, variables derived in the source data will not be re-calculated.

QMD Ref: [REDACTED]	Effective: 12Aug2019	Governing QMD: [REDACTED]
Confidentiality Statement		
This document is the property of [REDACTED] and may not be duplicated, copied, altered or removed from company without prior approval from [REDACTED] or in compliance with [REDACTED].		
REF: [REDACTED]		Page 11 of 37

		Controlled Quality Management Document	
		Sponsor:	Aurinia Pharmaceuticals
		Protocol Number:	AUR-VCS-2016-02
STATISTICAL ANALYSIS PLAN. PHASE 2-3-4			

6.2.1 Race

Where more than one race category has been selected for a subject, these race categories will be combined into a single category labeled “Multiple Race” in the summary tables. For black race category ‘Black (including mixed black)’ will be used.

6.2.2 Baseline

Except for parameters detailed later in this section, baseline is defined as the last non-missing value (either scheduled, unscheduled or repeat) before the subject receives the first dose of study drug on Day 1 in AURORA 1. As assessments on Day 1 in AURORA 1 are scheduled to be undertaken prior to taking study drug, Day 1 assessments can be defined as baseline.

eGFR baseline will be calculated as the lowest measurement available prior to dosing in AURORA 1.

Urine creatinine baseline will be calculated as the mean of the latest 2 pre-randomization values in AURORA 1. Should only 1 value be available, it will be used as the baseline value.

Urine protein baseline will be calculated as the mean of the latest 2 pre-randomization values in AURORA 1. Should only 1 value be available, it will be used as the baseline value.

UPCR values are calculated by the laboratory as the ratio of urine protein to creatinine. The ratio is only calculated where laboratory tests produce a result for both the creatinine and the protein. UPCR baseline will be calculated as the mean of the latest 2 pre-randomization values. Should only 1 value be available, it will be used as the baseline value.

For the endpoints of change from baseline in UPCR and also for partial response endpoints (that incorporate a 50% reduction from baseline in UPCR), a second definition of baseline (alternative baseline) UPCR will be defined as the lowest measurement available prior to dosing.

6.2.3 Early Terminations Assessments

Data collected at Early Termination (ET) assessments will be mapped to the visits closest to the date of termination.

QMD Ref: [REDACTED]	Effective: 12Aug2019	Governing QMD: [REDACTED]
Confidentiality Statement		
This document is the property of [REDACTED] and may not be duplicated, copied, altered or removed from company without prior approval from [REDACTED] or in compliance with [REDACTED].		

REF: [REDACTED]

		Controlled Quality Management Document	
		Sponsor:	Aurinia Pharmaceuticals
		Protocol Number:	AUR-VCS-2016-02
STATISTICAL ANALYSIS PLAN. PHASE 2-3-4			

6.2.4 Duration / Study Day / Time

Study day will be calculated as the number of days from first dose of study drug (Day 1) in AURORA 1.

- Date of event – date of first dose of study drug (in AURORA 1) + 1, for events on or after first dose
- Date of event – date of first dose of study drug (in AURORA 1), for events before first dose

To this end, Day 0 remains undefined.

For all time to event analyses, subjects not reporting the specified endpoint will be censored at the time that the subjects were last known not to have experienced the endpoint. For all endpoints not encompassing death, all deaths will be treated as censoring events. In complex cases where the censoring time of the subject is uncertain, the case will be reviewed by the [REDACTED] statistician and a censoring time will be assigned and programmed prior to database lock.

6.2.5 Conventions for Missing and Partial Dates

All rules explained below for partial/missing dates will be followed unless contradicted by any other data recorded on the electronic Case Report Form (eCRF).

All dates presented in the individual subject listings will be as recorded on the eCRF (i.e., not completed as per the below rules).

6.2.6 Missing / Partial Start / Stop Date of Adverse Events (AE) and Concomitant Medications

Missing and partial start and stop dates will be imputed for analysis purposes as follows:

Partial or missing stop date will be imputed as follows:

- If the stop date is completely missing and the event has resolved or the subject has stopped taking the concomitant medication, the stop date will be imputed as the date of the subject’s last clinic visit in the study.
- If only the year is known, the stop date will be imputed as “31-Dec” of that year or as the date of the subject’s last clinic visit in the study if in the same year.

QMD Ref: [REDACTED]	Effective: 12Aug2019	Governing QMD: [REDACTED]
Confidentiality Statement		
This document is the property of [REDACTED] and may not be duplicated, copied, altered or removed from company without prior approval from [REDACTED] or in compliance with [REDACTED].		

REF: [REDACTED]

		Controlled Quality Management Document	
		Sponsor:	Aurinia Pharmaceuticals
		Protocol Number:	AUR-VCS-2016-02
STATISTICAL ANALYSIS PLAN. PHASE 2-3-4			

- If the month and year are known, the stop date will be imputed as the last day of that month unless the stop date corresponds to the same month as the subject’s last clinic visit in which case the date of subject’s last clinic visit in the study will be used instead.

Missing start date will be imputed as follows:

- If the stop date occurs on or after the start of study drug in AURORA 2 or the event/concomitant medication is ongoing, the start date will be imputed as the date of the first dose of study drug in AURORA 2.
- If the stop date occurs before the start of study drug in AURORA 2, the start date of the event/concomitant medication will be imputed as the subject’s AURORA 1 Visit 15 (Week 52) date or the stop date of the event/concomitant medication whichever the earlier.

Partial start date (year present, but month and day missing)

- If the stop date occurs on or after the start of study drug in AURORA 2 or the event/concomitant medication is ongoing at the end of AURORA 1, and the year is the same as the year of first dosing in AURORA 2 the start date will be imputed as “01-Jan” of the same year or the date of the first dose of study drug in AURORA 2 whichever is latest. If the year is different from the year of first dosing “01-Jan” will be used.

If the stop date occurs before the start of study drug in AURORA 2, the start date of the event/concomitant medication will be imputed as the “01-Jan” of the same year.

Partial start date (month and year present, but day missing)

- If the stop date occurs on or after the start of study drug in AURORA 2 or the event/concomitant medication is ongoing, the start date will be imputed as the first day of the same month and year unless this partial start date is in same month as the first dose of study drug in AURORA 2 in which case the date of first dose of study drug in AURORA 2 will be used.

If the stop date occurs before the start of study drug in AURORA 2, the start date will be imputed as the first day of the month and year of the partial stop date.

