## **13.9 Safety Evaluations**

Specific safety endpoints are as follows:

- Biochemical (including liver function tests) and hematological laboratory tests
- AE profile and routine biochemical and hematological safety parameters
- Vital signs (BP, HR, temperature) at specific time points and change from baseline
- Standard 12-lead ECGs change from baseline
- Discontinuations from treatment
- Concomitant medications

Laboratory values, vital signs, and other safety parameters providing numeric data will be summarized by visit as absolute values and change from baseline. Laboratory values outside of defined normal ranges will be summarized.

Adverse events will be coded using the latest available version of the Medical Dictionary for Regulatory Activities, the version of which will be provided in the clinical study report.

Treatment-emergent adverse events will be summarized by treatment arm, system organ class, and preferred term. SAEs, SAEs that led to death, and SAEs/AEs that led to withdrawal will also be summarized and listed.

Only AEs which started on or after the date of first dose of study treatment in AURORA 2 will be considered TEAEs, though all AEs after informed consent will be recorded. SAEs occurring at any time after informed consent will be summarized. All concomitant medications will be summarized.

Details of these and other analyses will be provided in the SAP.

All study data analyses involving laboratory values will be based on results from the central laboratory.

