6.8 Prior and Concomitant Medications

Separate tabulations will be produced for prior and concomitant medications presented by treatment group and overall for the safety population. Medications will be summarized using ATC Level 2.

Additionally, prior and concomitant medications will be summarized for subjects who did not continue to AURORA 2.

Prior medications are defined as all medications starting and stopping before the date of first dose of study drug in AURORA 1.

Prior and concomitant medications are defined as both:

- **Concomitant Medications Ongoing at the First Dose of AURORA 1:** medications starting before AURORA 1 and continuing at the time of starting AURORA 1.
- **Concomitant Medications Ongoing at the end of AURORA 1:** medication starting before AURORA 2 and continuing at the time of starting AURORA 2.

Concomitant medications are defined as medications starting on or after the date of first dose of study drug in AURORA 2.

QMD Ref: [REDACTED]	Effective: 12Aug2019	Governing QMD: [REDACTED]
Confidentiality Statement		
This document is the property of [REDACTED] and may not be duplicated, copied, altered or removed from company without prior approval from [REDACTED] or in compliance with [REDACTED].		

REF: [REDACTED]

		Controlled Quality Management Document	
		Sponsor:	Aurinia Pharmaceuticals
		Protocol Number:	AUR-VCS-2016-02
STATISTICAL ANALYSIS PLAN. PHASE 2-3-4			

The following previous LN therapies will also be summarized: MMF, Intravenous Cyclophosphamide, Corticosteroids, Methotrexate, Calcineurin Inhibitors, Biologics, Azathioprine, Antimalarials, other. The responses for these LN therapies are Yes or No.

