This document is the property of [REDACTED] and may not be duplicated, copied, altered or removed from company without prior approval from [REDACTED] or in compliance with [REDACTED].		

REF: [REDACTED]

		Controlled Quality Management Document	
		Sponsor:	Aurinia Pharmaceuticals
		Protocol Number:	AUR-VCS-2016-02
STATISTICAL ANALYSIS PLAN. PHASE 2-3-4			

- Serious TEAE by System Organ Class, Preferred Term and Severity
- Treatment-Related, Serious TEAE by System Organ Class and Preferred Term
- Treatment-Related, Serious TEAE by System Organ Class, Preferred Term and Severity
- Serious TEAE by System Organ Class and Preferred Term Leading to Dose Modification
- Serious TEAE by System Organ Class and Preferred Term Leading to Voclosporin/Placebo Discontinuation
- Disease-Related, Serious TEAE by System Organ Class and Preferred Term

The following displays of AURORA 2 TEAEs will also be presented:

- Treatment-Emergent Adverse Events by Descending Frequency of Preferred Term
- Non-Serious Treatment-Emergent Adverse Events Occurring at an Incidence of >2% by Descending Frequency, System Organ Class and Preferred Term
- Treatment-Emergent Adverse Events by Descending Difference of Preferred Term between Treatment Group
- Listing of Serious TEAE
- Listing of TEAE Resulting in Death
- Listing of Post-Treatment Adverse Events Resulting in Death

The following displays will include all TEAEs from the start of AURORA 1:

- TEAE by System Organ Class and Preferred Term by Year of Onset
- Treatment-Related TEAE by System Organ Class, Preferred Term and Year of Onset
- TEAE by System Organ Class and Preferred Term Leading to Dose Modification by year of onset
- Serious TEAE by System Organ Class and Preferred Term by Year of Onset
- Treatment-Related, Serious TEAE by System Organ Class and Preferred Term and Year of onset
- Serious TEAE by System Organ Class and Preferred Term Leading to Dose Modification by year of onset

The following displays will be presented for all randomized subjects from Aurora 1?

- TEAE by System Organ Class and Preferred Term
- Serious TEAE by System Organ Class and Preferred Term

QMD Ref: [REDACTED]	Effective: 12Aug2019	Governing QMD: [REDACTED]
Confidentiality Statement		
This document is the property of [REDACTED] and may not be duplicated, copied, altered or removed from company without prior approval from [REDACTED] or in compliance with [REDACTED].		

REF: [REDACTED]

		Controlled Quality Management Document	

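### A year-only start flagged as ongoing at the end of AURORA 1 is imputed to the first AURORA 2 dose and so becomes an AURORA 2 TEAE; separately, no start-date rule uses the first AURORA 1 dose

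*SAP*

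**What the plan says.** SAP 6.2.6 handles incomplete start dates of AEs and concomitant medications in three groups.

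- **Year only.** One branch covers a record that stopped on or after the start of AURORA 2 drug, with the alternative trigger "event/concomitant medication is ongoing at the end of AURORA 1, and the year is the same as the year of first dosing" (AURORA 2 dosing). The start then becomes 1 January "of the same year or the date of the first dose of study drug in AURORA 2 whichever is latest". In the opposite case ("If the year is different from the year of first dosing"), the rule uses 1 January of the recorded year. Records that stopped before AURORA 2 also take 01-Jan of the recorded year.
- **Month and year.** A record that is ongoing, or that stopped on or after the start of AURORA 2 drug, takes the first of the month "unless this partial start date is in same month as the first dose of study drug in AURORA 2", when that dose date is used. One that stopped sooner takes the first day of the stop month.
- **Completely missing.** A record that is ongoing, or that stopped on or after the start of AURORA 2 drug, takes the first AURORA 2 dose. One that stopped sooner takes the earlier of AURORA 1 Visit 15 and the stop date.

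SAP 6.2.5 lets other eCRF data overrule any of these rules.

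The classifications that depend on these dates are in three places. Protocol 13.9 says: "Only AEs which started on or after the date of first dose of study treatment in AURORA 2 will be considered TEAEs". SAP 6.8 keeps a separate class for "medication starting before AURORA 2 and continuing at the time of starting AURORA 2"; a drug started on or after the first AURORA 2 dose is simply concomitant. The adverse-event section of the SAP (6.12.1 in its contents list) plans AURORA 2 TEAE tables and a second set: "The following displays will include all TEAEs from the start of AURORA 1".

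**The concern.** The year-only rule is triggered by a fact that settles the order of events, and then assigns a date that ignores it. A record flagged as ongoing at the end of AURORA 1 had begun by then. Dating it to the first AURORA 2 dose makes it new in AURORA 2. The AE profile is the primary endpoint (Protocol 3.3.1, SAP 3.1), so carried-over events would enter the main safety comparison, and drugs already in use would be shown as started in AURORA 2.

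The second issue is a missing guard. The SAP stops a partial date from falling just before the AURORA 2 dose, but has no such floor at the first AURORA 1 dose. SAP 6.2.4 counts study day from that dose, and the Month 0 to 36 tables start there. An on-treatment AE from the AURORA 1 dosing year could therefore be dated before any study drug.

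**Working it through.** **Inputs.** The rules above. AURORA 1 treatment lasts 52 weeks, or 364 days (SAP 1). The visit window is ±10 days (Protocol, Schedule of Events), used here as an assumed range of 354 to 374 days between the two first doses. Calendar years are illustrative. The plan states no figure of its own to reproduce. Write D1 and D2 for the first doses in AURORA 1 and AURORA 2.

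**Step 1: year-only start, recorded year = year of D2.** Imputed start = max(01-Jan of that year, D2). D2 lies in that year, so it is never before 01-Jan and the result is D2. The two options coincide only when D2 is itself 01-Jan. As a check, every D1 in 2017 to 2019 (3 × 365 = 1,095 dates) with gaps of 354, 364, 365 and 374 days gives 1,095 × 4 = 4,380 combinations. The result is D2 in all 4,380, so the 01-Jan option never changes it.

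**Step 2: classification.** Protocol 13.9 requires start ≥ D2. An imputed start of D2 satisfies it, so the AE is an AURORA 2 TEAE. For a drug, the class in SAP 6.8 for carried-over treatment requires start < D2. An imputed start of D2 fails it, and the drug becomes concomitant in AURORA 2.

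**Step 3: recorded year = year of D1.** The imputed start is 01-Jan, which precedes D1 unless D1 is 01-Jan. Counts are of possible dosing dates in an ordinary year.

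- Stopped before AURORA 2: 364/365 = 99.7% are dated before treatment.
- Still present in AURORA 2: 364/365 at the tested gaps of 364, 365 and 374 days, and 354/365 = 97.0% at 354 days. The 11 exceptions at 354 days are subjects first dosed on 1 to 11 January, whose two first doses fall in the same year.
- Month-only start in the month of D1, still present in AURORA 2: the first of the month precedes D1 for 29/30 = 96.7% of dosing days in a 30-day month.

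These are shares of dosing dates, not event rates.

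**Step 4: one subject, D1 = 15-Jun-2018, D2 = 14-Jun-2019 (364 days later).**

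| Recorded start | Status | Imputed start | Position |
|---|---|---|---|
| 2019 | ongoing at end of AURORA 1 | 14-Jun-2019 | AURORA 2 TEAE |
| 2018 | ongoing | 01-Jan-2018 | before D1 |
| 2018 | stopped Dec-2018 | 01-Jan-2018 | before D1 |
| Jun-2018 | ongoing | 01-Jun-2018 | before D1 |
| 2019 | stopped Mar-2019 | 01-Jan-2019 | AURORA 1, on treatment |
| missing | stopped 01-Dec-2018 | 01-Dec-2018 | AURORA 1, on treatment |

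In the first row the possible onset days run from 1 January to 14 June: 31 + 28 + 31 + 30 + 31 + 14 = 165. All but the last, 164, lie before D2, yet the rule picks the last. The final two rows come out correctly.

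**The case against.** **The override.** SAP 6.2.5 makes every rule yield to contradicting eCRF data, and the ongoing flag is such data. But that flag is also a stated trigger of the rule, so the text prescribes and forbids the same imputation. It gives no replacement date. Where 01-Jan falls before the subject's consent, the override might also block some pre-treatment dates, again without saying what to use.

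**A slip of wording.** The other two groups say only that the record is ongoing, so the reference to the end of AURORA 1 may be a drafting error in an otherwise conservative default. That is plausible, and the default is reasonable when timing relative to AURORA 2 is unknown. Deleting the words would not be enough, because a record carried over from AURORA 1 would still meet the plain ongoing trigger.

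**The Month 0 to 36 tables.** The available text does not say that TEAEs in those tables are counted from the first AURORA 1 dose. The opening of SAP 6.12.1, where a definition could stand, is missing from that text, which is not a fault of the plan. SAP 6.2 also says that variables derived in the source data are not recalculated unless otherwise stated, so AURORA 1 dates may be carried over as they are. This objection stands: the second issue is conditional.

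**Rarity.** Onset dates are required (Protocol 10.3.1), incomplete data are queried (Protocol 16.2.1), the rule is the same in both arms, and listings show dates as recorded. This limits the size but does not correct the rule.

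**Conclusion.** The year-only rule is wrong as written, and this follows from the text alone. For a record flagged ongoing at the end of AURORA 1, with a recorded year equal to the AURORA 2 dosing year, it always returns the first AURORA 2 dose. The second issue holds only if Month 0 to 36 TEAEs are defined from the first AURORA 1 dose and AURORA 1 dates are imputed under this SAP. In that case the affected starts are nearly always dated before treatment. The number of partial dates is not given, and the effect is probably small.

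A reader might infer more, and the documents do not support it:

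- *All start dates are anchored on the AURORA 2 dose, or every carried-over event becomes an AURORA 2 TEAE.* Other branches use Visit 15, the stop date, 01-Jan or the first of the month. A year-only record with an earlier year stays out of AURORA 2.
- *Every flagged record is misdated.* Visit 15 ends AURORA 1 and is also the visit at which AURORA 2 drug is dispensed, so an onset on that day could fit both.
- *Renal response is affected through misdated prednisone above 10 mg.* Corticosteroid doses and adjustments must be recorded (Protocol 7.5.3), and SAP 6.9 expects prescription records to cover each study day. A year-only steroid record that decides a response is not shown.
- *The exposure-adjusted tables lose events.* SAP 6.12.1.1 includes all events from both studies, not only TEAEs.
- *Most pre-dated AEs were truly on treatment.* The documents give neither the AURORA 1 screening length nor its AE collection start, so no share can be stated.

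**What to change.** 1. For a record flagged ongoing at the end of AURORA 1 with a year-only start in the AURORA 2 dosing year, impute the later of 01-Jan of that year and the first AURORA 1 dose, and no later than the day before the first AURORA 2 dose. If the first AURORA 2 dose is on 01-Jan, the recorded year leaves no earlier day, so keep 01-Jan. In the example above, the first row becomes 01-Jan-2019, on treatment in AURORA 1.
2. For AEs in the Month 0 to 36 and all-randomized TEAE displays, when the recorded year (or month and year) is that of the first AURORA 1 dose and the AE is not known to have started or ended before that dose, impute no earlier than that dose. State the TEAE definition for these displays, and whether AURORA 1 dates are re-imputed or carried over.
3. Keep the AURORA 2 anchor for records whose timing relative to AURORA 2 is truly unknown, and leave year-only records with other, earlier years unchanged. Without that year condition, drugs started years before would be moved to the first AURORA 1 dose.

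The cost is a few lines of SAP text and one more anchor date in the imputation program. The downside is that a few doubtful early events will count as AURORA 1 TEAEs, and an event that truly began on the changeover day will be placed in AURORA 1. The first is the same cautious choice that the SAP already makes around the AURORA 2 dose.
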